Appendix III. Functional Assessment of Cancer Therapy-Endocrine Subscale (FACT-ES)

FACT-ES (Version 4)

Please circle or mark one number per line to indicate your response as it applies to the past 7 days.

	ADDITIONAL CONCERNS	Not at all	A little bit	Some-what	Quite a bit	Very much
ES1	I have hot flashes/hot flushes	0	1	2	3	4
ES2	I have cold sweats	0	1	2	3	4
ES3	I have night sweats	0	1	2	3	4
ES4	I have vaginal discharge.....	0	1	2	3	4
ES5	I have vaginal itching/irritation.....	0	1	2	3	4
ES6	I have vaginal bleeding or spotting	0	1	2	3	4
ES7	I have vaginal dryness	0	1	2	3	4
ES8	I have pain or discomfort with intercourse.....	0	1	2	3	4
ES9	I have lost interest in sex	0	1	2	3	4
ES10	I have gained weight	0	1	2	3	4
An9	I feel lightheaded (dizzy).....	0	1	2	3	4
O2	I have been vomiting.....	0	1	2	3	4
C5	I have diarrhea (diarrhoea)	0	1	2	3	4
An10	I get headaches	0	1	2	3	4
Tax1	I feel bloated.....	0	1	2	3	4
ES11	I have breast sensitivity/tenderness	0	1	2	3	4
ES12	I have mood swings.....	0	1	2	3	4
ES13	I am irritable	0	1	2	3	4
BRM1	I have pain in my joints	0	1	2	3	4

Appendix IV. Pittsburgh Sleep Quality Index (PSQI)

The Pittsburgh Sleep Quality Index

Name _____

Date _____

Instructions:

The following questions relate to your usual sleep habits during the past month *only*. Your answers should indicate the most accurate reply for the *majority* of days and nights in the past month. Please answer all the questions.

1. During the past month, when have you usually gone to bed at night?

usual bed time _____

2. During the past month, how long (in minutes) has it usually taken you to fall asleep each night?

number of minutes _____

3. During the past month, when have you usually got up in the morning?

usual getting up time _____

4. During the past month, how many hours of *actual* sleep did you get at night? (This may be different than the number of hours you spend in bed).

hours of sleep per night _____

For each of the remaining questions, check the one best response. Please answer *all* questions.

5. During the past month, how often have you had trouble sleeping because you.....

- (a) Cannot get to sleep within 30 minutes

Not during the past month _____	Less than once a week _____	Once or twice a week _____	three or more times a week _____
---------------------------------	-----------------------------	----------------------------	----------------------------------

- (b) Wake up in the middle of the night or early morning

Not during the past month _____	Less than once a week _____	Once or twice a week _____	Three or more times a week _____
---------------------------------	-----------------------------	----------------------------	----------------------------------

- (c) Have to get up to use the bathroom

Not during the past month _____	Less than once a week _____	Once or twice a week _____	three or more times a week _____
---------------------------------	-----------------------------	----------------------------	----------------------------------

- (d) Cannot breathe comfortably

11/8/2019

Not during the past month_____	Less than once a week_____	Once or twice a week_____	three or more times a week_____
--------------------------------	----------------------------	---------------------------	---------------------------------

(e) Cough or snore loudly

Not during the past month_____	Less than once a week_____	Once or twice a week_____	three or more times a week_____
--------------------------------	----------------------------	---------------------------	---------------------------------

(f) Feel too cold

Not during the past month_____	Less than once a week_____	Once or twice a week_____	three or more times a week_____
--------------------------------	----------------------------	---------------------------	---------------------------------

(g) Feel too hot

Not during the past month_____	Less than once a week_____	Once or twice a week_____	three or more times a week_____
--------------------------------	----------------------------	---------------------------	---------------------------------

(h) Had bad dreams

Not during the past month_____	Less than once a week_____	Once or twice a week_____	three or more times a week_____
--------------------------------	----------------------------	---------------------------	---------------------------------

(i) Have pain

Not during the past month_____	Less than once a week_____	Once or twice a week_____	three or more times a week_____
--------------------------------	----------------------------	---------------------------	---------------------------------

(j) Other reason(s), please describe_____

How often during the past month have you had trouble sleeping because of this?

Not during the past month_____	Less than once a week_____	Once or twice a week_____	three or more times a week_____
--------------------------------	----------------------------	---------------------------	---------------------------------

6. During the past month, how would you rate your sleep quality overall?

Very good_____
Fairly good_____
Fairly bad_____
Very bad_____

7. During the past month, how often have you taken medicine (prescribed or “over the counter”) to help you sleep?

Not during the past month_____ Less than once a week_____ Once or twice a week_____ three or more times a week_____

8. During the past month, how often have you had trouble staying awake while driving, eating meals, or engaging in social activity?

Not during the past month_____ Less than once a week_____ Once or twice a week_____ three or more times a week_____

9. During the past month, how much of a problem has it been for you to keep up enough enthusiasm to get things done?

No problem at all_____
Only a very slight problem_____
Somewhat of a problem_____
A very big problem_____

10. Do you have a bed partner or roommate?

No bed partner or roommate_____
Partner/roommate in other room_____
Partner in same room, but not same bed_____
Partner in same bed_____

11. How often do you feel tired during the following times during the day?

Morning:

0 most days	1 often	2 occasionally	3 never
----------------	------------	-------------------	------------

Afternoon:

0 most days	1 often	2 occasionally	3 never
----------------	------------	-------------------	------------

Evening:

0 most days	1 often	2 occasionally	3 never
----------------	------------	-------------------	------------

11/8/2019

Appendix V. Acupuncture Expectation Scale

Name of participant: _____
Date: _____

ACUPUNCTURE EXPECTATION SCALE

Every individual may have different expectation for the effects of acupuncture. If we use the following sentences to describe your expectation of acupuncture's effect on your hot flash symptoms after the entire course of acupuncture therapy, how much do you agree? For each statement, please choose the closest answer.

	Not at all agree	A little agree	Moderately agree	Mostly agree	Completely agree
My hot flash symptoms will improve a lot	1	2	3	4	5
I will be able to cope with my hot flash symptoms better	1	2	3	4	5
The symptoms of my hot flashes will disappear	1	2	3	4	5
My energy level will increase	1	2	3	4	5

Appendix VI. Acupuncture Treatment Form

Name of patient: _____ Hospital ID# : _____ Date of Visit : _____ Number of Sessions: _____ out of 12/6

1. Please make “X” below to indicate the points used, *De Qi* sensation, and electro-stimulation used at today’s session:

Points	LR3	K3	SP6	ST36	CV6	HT7	LI11	GV20	Y.T.	S.M.	Heart	Note
L												
R												
DeQi												
e-stim												

2. Please record on the line below regarding the electroacupuncture parameters used at today’s session:

Frequency: _____ Hz; Pulse width: _____ (40/350)µS; Pulse mode: _____ (DD/Conti.)

3. Please ask the study patient when you have just completed the adjustment of during the treatment session today and make a “X” below: “Please tell me, on a scale from 0 to 10, the intensity of the needling sensation you are experiencing right now; 0 is that you do not feel anything at all and 10 is the strongest sensation you could imagine.”

Intensity Score	0	1	2	3	4	5	6	7	8	9	10
X											

4. At the end of the session, please make “X” below on the patient’s immediate responses for today’s treatment:

	Question Items	Yes	No	Unknown
a	Did the patient appear to be relaxed?			
b	Was the patient dozed off during the treatment?			
c	Did the patient still feel the “tapping” sensation at the end of the session?			
d	Was the pulse/heart rate of the patient slower than the beginning of the session?			
e	Has the patient’s skin temperature of hands noticeably changed (either warmed up or cooled down)?			
	Other observations?			

5. Did the patient report any adverse event per CTCAE v4.0 at this visit? Please make a circle below:

NO YES, If “YES” is answered, please describe the details here:

Adverse Event	Start Date	Stop Date	Grade (1-5) Mild, Moderate, Severe, Life Threatening, Fatal	Attribution	Comments
Skin bruise					
Hematoma					
Skin infection					
Presyncope					
Syncope					
Nausea					

6. Was today's session completely followed the study protocol requirement?

Question Item	YES	NO	If "no", please explain here
Was today's session completely followed the study protocol requirement?			

Signature of acupuncturist

Name of acupuncturist

11/8/2019

Appendix VII. Medication Log

Date: _____

The following are possible medications or supplements you might be using at home after chemotherapy. You might be taking medications that are not in the list as well. Please indicate ALL prescription medications AND over-the-counter medications you have taken at home **in the past 5 days.**

Medication Treatment Log

Name of Medication	Did you take any of these?		Dose of each pill (5 mg? or 10 mg?)	How MANY pills did you take EACH TIME?	How OFTEN did you take it EACH DAY?	Date Started (MM/DD/YY)	Date Stopped (MM/DD/YY)	For staff use only Total dose in the past 5 days
Tamoxifen	Y	N						
Fulvestrant (Faslodex)	Y	N						
Anastrozole (Arimidex)	Y	N						
Letrozole (Femara)	Y	N						
Exemestane (Aromasin)	Y	N						
Gosrelin (Zoladex)	Y	N						
Leuprolide (Lupron)	Y	N						
Clonidine (Catapres)	Y	N						
Methyldopa	Y	N						
Venlafaxine (Effexor)	Y	N						
Escitalopram (Lexapro)	Y	N						
Paroxetine (Paxil)	Y	N						
Fluoxetine (Prozac)	Y	N						
Gabapentin (Neurontin)	Y	N						
Duloxetine (Cymbalta)	Y	N						
Pregabalin (Lyrica)	Y	N						
Dietary Supplements:	Y	N						
	Y	N						
	Y	N						
	Y	N						
Herbs:	Y	N						
	Y	N						

11/8/2019

Appendix IX. Study Flyer

Hot flashes are common in women being treated for breast cancer.

[figure not shown]
This study is being done to see if acupuncture treatments can help reduce hot flashes.

Talk to your doctor about whether this study is a good fit for you.

**SUSAN F. SMITH
CENTER FOR
WOMEN'S CANCERS**

Are you receiving hormone therapy for breast cancer?

For more information, please contact:

[Study Coordinator]

[CRC Phone Number]

[CRC Email Address]

Principal Investigator:

[name], MB, MPH, PhD
1/19/2024 10:28 AM
(Dana-Farber)

The Acupuncture for Hot Flashes Study

Ask your doctor about

A Dana-Farber study for Hot Flashes associated with hormone therapy

Frequently Asked Questions

You may be able to join this study if:

- ✓ You have already completed any planned chemotherapy and/or surgery

- ✓ You are currently receiving hormone therapy for stage I-III breast cancer, for example:

- Tamoxifen (Nolvadex, Soltamox)
- Anastrozole (Arimidex)

- Letrozole (Femara)

- Exemestane (Aromasin)
- Other hormone therapies

Study participants will be **randomly** assigned to one of the following groups:

- Acupuncture is a complementary therapy in which thin, sterile, disposable needles are inserted into various spots on the body with the goal of reducing hot flashes.

Can I choose my treatment schedule?

- No – you will be randomly assigned to one of the two groups. You should only agree to participate if you are willing to follow *either* schedule.

Delayed Acupuncture Group

- Initial 10-week delay
- 10-week acupuncture treatment schedule (10 total sessions)

- ✓ You are experiencing persistent Hot Flashes

If I join, what do I have to do?

- ✓ Keep a Hot Flash diary
- ✓ Complete a series of questionnaires
- ✓ Undergo a blood draw before you start and at week 10
- ✓ Follow the assigned acupuncture schedule

Appendix X. Recruitment Language for DFCI Listservs

Do you experience frequent hot flashes while receiving hormonal therapy for breast cancer? If yes, you may be eligible for a study investigating whether acupuncture treatments can help reduce the frequency and severity of hot flashes in women receiving hormonal therapy for breast cancer. You may be able to join this study if:

- You have completed any planned chemotherapy and/or surgery for your breast cancer
- You are currently receiving hormonal therapy for stage I-III breast cancer, for example:
 - Tamoxifen (Nolvadex, Soltamox)
 - Anastrozole (Arimidex)
 - Letrozole (Femara)
 - Exemestane (Aromasin)
 - Other hormonal therapies
- You are experiencing persistent hot flashes

If you are interested in participating or would like to learn more about this study, please contact the research manager at [contact] or [contact].

Appendix XI. Information on Rally at Partners Healthcare

Headline: Do you experience frequent hot flashes while receiving hormonal therapy for breast cancer?

Summary

We are studying whether acupuncture treatments can help reduce the frequency and severity of hot flashes in women receiving hormonal therapy for breast cancer.

Custom URL: https://rally.partners.org/study/acupuncture_hot_flash

Category

- Breast Cancer
- Acupuncture
- Hormones

Project Image

Funding Source: Other

At which institutions is the project being conducted? Dana Farber Cancer Institute

IRB Organization Dana Farber Cancer Institute

IRB Protocol Number 18-371

Recruitment Start Date 02/01/2019

Recruitment End Date 02/29/2020

Team

Principal Investigator [name], MB, PhD, MPH

Email Address (for internal use only) [contact]

Phone Number (for internal use only) [name]

PI Organization Dana Farber Cancer Institute

Project Contact [name], [contact], [name]

Research

What are you studying?

This study is being done to see if acupuncture can help reduce the number and intensity of hot flashes and night sweats that women experience during breast cancer treatment. Hot flashes and night sweats are common side effects of hormonal medications like tamoxifen and aromatase inhibitors that are used to treat breast cancer. These symptoms can affect mood, sleep, and quality of life. Though prescription medications can reduce hot flashes and night sweats for some

11/8/2019

patients, they are not helpful for all patients and can sometimes cause other side effects. New treatments are needed to help reduce hot flashes and night sweats in women with breast cancer.

Why is it important?

Acupuncture is a complementary therapy in which hair-thin, sterile disposable needles are inserted into various spots on your skin, with the goal of affecting body's natural healing system. Acupuncture has been tested in clinical trials in cancer patients and has been shown to be helpful in treating a number of side effects of cancer treatment, such as nausea and vomiting from chemotherapy. A few early studies have suggested that acupuncture may help to lessen hot flashes, but more information is needed about the benefits of acupuncture in breast cancer patients.

Clinical Trial Phase: This project does not study a drug or biologic product. Not applicable.

Eligibility

Who can participate?

- Women with a history of Stage I-III hormone-receptor positive breast cancer;
- Must have completed all primary chemotherapy and surgery; Must be receiving hormonal therapy (e.g. Tamoxifen and/or Aromatase inhibitors) with or without ovarian function suppression for at least 4 weeks at study entry;
- Must have persistent hot flashes for at least 4 weeks AND have more than 14 episodes of hot flashes per week (2 hot flashes per day) during the week prior to the study entry.

Who cannot participate?

- Cannot be undergoing chemotherapy or planned surgery during the study period;
- Cannot change hormonal therapy regimen during the study period;
- Cannot have used acupuncture for hot flashes within 6 months prior to the study entry;
- Cannot be starting a new medication-based treatment for hot flashes, such as selective serotonin reuptake inhibitors (SSRIs) and/or anti-convulsant for less than 4 weeks prior to study entry. Participants may continue with medications or therapies for the treatment of hot-flashes while participating in the study if the medication has been taking for more than 4 weeks prior to study entry AND the dose of the medication is going to be kept consistently during the study.

Age: 18 years or older

Gender: Female

Participation Details

Estimated time commitment: 20 sessions over 10 weeks

What may participants be asked to do?

If you decide to participate, you will be involved in the study for about 20 weeks. Participants will be randomly assigned to one of two groups – an immediate acupuncture group or a delayed acupuncture group.

11/8/2019

- The immediate acupuncture group will receive 20 acupuncture sessions over the first 10 weeks after joining the study.
- The delayed acupuncture group will receive 10 acupuncture treatments after a 10-week waiting period.
- All acupuncture treatments will be administered by Zakim Center staff acupuncturists trained on the study.

We will collect various measures throughout the study.

- Medical history & questionnaires. Participants will be asked to complete questionnaires, a medication log, and a hot flash diary at various time points throughout the study.
- Blood tests. There are two study-associated blood draws.
- One at Baseline and one at Week 10. Activity tracker. Participants will be asked to wear an activity tracker watch for a full week at Baseline, Week 10, and Week 20.

Does your project involve any of the following activities?

- Survey
- Personal health tracking
- Blood draw
- Office visit

Travel Requirements

- Accessible by public transportation
- Parking available
- Parking reimbursed

Where will participants need to go?

Zakim Center for Integrative Therapies and Healthy Living, [name]

Benefits and Compensation

What will participants receive?

- Participants may receive up to 20 acupuncture sessions, depending on their randomization group.
- Participants will receive a voucher to cover parking after each acupuncture treatment session or study-related visit.
- Participants will receive a \$10 gift card at Week 10 in exchange for the completion of all study-related surveys and logs required from Baseline to Week 10.
- Participants will receive an additional \$10 gift card at Week 20 in exchange for the completion of all study-related surveys and logs required from Week 10 to Week 20.

Select all that apply: Gift card

Dollar Amount (up to): \$20.00

11/8/2019

Appendix XIII. Sleep Diary

Protocol #: 18-371

Participant ID: _____

Weekly Sleep Diary (Please complete upon awakening)

	Sample	Day 1 MM DD YY	Day 2 MM DD YY	Day 3 MM DD YY	Day 4 MM DD YY	Day 5 MM DD YY	Day 6 MM DD YY	Day 7 MM DD YY
1. What time did you get into bed to try to go to sleep?	10:15 p.m.							
2. How long did it take you to fall asleep?	55 min							
3a. How many times did you wake up, not counting your final awakening?	6 times							
3b. In total, how long did these awakenings last?	2 hours 5min							
4. What time was your final awakening?	6:35 a.m.							
5a. How many times did you nap or doze?	2 times							
5b. In total, how long did you nap or doze?	1 hour 10 min							
6. Did you have any hot flash(es) that interfered with your sleep? If yes, how many?	() No (x) Yes (x) 1-2 () 3-4 () 5 or more							

Adopted from the Consensus Sleep Diary
Carney et al. *Sleep* 2012

1/19/2024 10:28 AM

Appendix XIV. Insomnia Severity Index

Insomnia Severity Index

For each question, please mark the number that best describes your answer. Please rate the CURRENT (i.e. LAST MONTH) SEVERITY of your insomnia problem(s).

Insomnia Problem	None	Mild	Moderate	Severe	Very Severe
1. Difficulty falling asleep	0	1	2	3	4
2. Difficulty staying asleep	0	1	2	3	4
3. Problems waking up too early	0	1	2	3	4

4. How SATISFIED/DISSATISFIED are you with your CURRENT sleep pattern?

Very Satisfied Satisfied Moderately Satisfied Dissatisfied Very Dissatisfied
0 1 2 3 4

5. How NOTICEABLE to others do you think your sleep problem is in terms of impairing the quality of your life?

Not at all Noticeable A Little Somewhat Much Very Much Noticeable
0 1 2 3 4

6. How WORRIED/DISTRESSED are you about your current sleep problem?

Not at all Worried A Little Somewhat Much Very Much Noticeable
0 1 2 3 4

7. To what extent do you consider your sleep problem to INTERFERE with your daily functioning (e.g. daytime fatigue, mood, ability to function at work/daily chores, concentration, memory, mood, etc.) CURRENTLY?

Not at all Interfering A Little Somewhat Much Very Much Noticeable
0 1 2 3 4

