The primary endpoint will be the change in mean weekly hot flash score from baseline to week 10 between the two arms. The secondary endpoints will include changes from baseline in mean weekly hot flash score at week 20; and the mean total scores and subscores of Functional Assessment of Cancer Therapy- Breast Cancer (FACT-B), the Endocrine Subscale (FACT-ES); and the Pittsburgh Sleep Quality Index (PSQI) at week 10, and week 20 between two arms; changes in mean weekly hot flash score in the high dose (immediate) acupuncture arm and the low dose (control) acupuncture will also be compared. Other secondary endpoints include changes in Insomnia Severity Index (ISI) score as well as changes in sleep efficiency, onset latency, number and duration of awakenings, and number of nighttime hot flashes interfering with sleep, as assessed by the sleep diary, from baseline to week 10 and week 20. Tertiary endpoints will include assessment changes in NF-κB, STAT-1 and STAT-3, and associated cytokines including IL-8, TNF- α , IL-6, and T-cells in the two study arms. NCI Common Terminology Criteria for Adverse Events (CTCAE) version 4.03 will be utilized for safety reporting.

Figure 1. Study schema

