7.11 Insomnia Severity Index

Insomnia Severity Index (ISI) is a widely used, validated patient-reported questionnaire for assessing insomnia severity.⁶⁵ It is composed of 7 questions, each scored on a 5-point scale (range 0-4) and the total scores ranging from 0 to 28. Higher scores correspond to a more severe insomnia and an 8-point reduction are considered clinically meaningful. The ISI will be collected at three time points: baseline, at week 10, and week 20.

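### In Appendix XIV, the top response label of Insomnia Severity Index items 6 and 7 repeats item 5's label and does not match what those items ask

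*Combined protocol and SAP*

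**What the plan says.** Section 7.11 describes the ISI as a validated questionnaire: "It is composed of 7 questions, each scored on a 5-point scale (range 0-4"). It gives a total of 0 to 28 and calls an 8-point reduction clinically meaningful. The form is completed at baseline, week 10 and week 20. Section 5 makes it an endpoint: "Other secondary endpoints include changes in Insomnia Severity Index (ISI) score", and Section 10.2 also lists it among the secondary endpoints.

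Appendix XIV prints the form. Its last three items read as follows.

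- Item 5: "How NOTICEABLE to others do you think your sleep problem is in terms of impairing the quality of your life", answered on "Not at all Noticeable A Little Somewhat Much Very Much Noticeable".
- Item 6: "How WORRIED/DISTRESSED are you about your current sleep problem", answered on "Not at all Worried A Little Somewhat Much Very Much Noticeable".
- Item 7: "To what extent do you consider your sleep problem to INTERFERE with your daily functioning", answered on "Not at all Interfering A Little Somewhat Much Very Much Noticeable".

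Each line is numbered 0 to 4, and participants are told to mark a number.

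**The concern.** On items 6 and 7 the bottom label follows the question, but the top label does not. A participant who is extremely worried, or badly impaired during the day, but whose sleep problem nobody else sees, finds no top option that describes her. She may mark 4 by reading the label simply as the end of the scale, or she may mark 3. The reverse is also possible: someone whose problem is obvious to others may be drawn to 4 on an item about worry.

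At stake is some measurement error in the highest category of two items in a secondary endpoint. There is also a form whose wording is inconsistent without explanation. Section 7.4 states and justifies the change it makes to the recall period of the Pittsburgh Sleep Quality Index. Nothing comparable is said about the ISI, so the labels look unintended.

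**Working it through.** **1. Each question against its end labels (Appendix XIV).**

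| Item | Construct asked | Bottom label (0) | Top label (4) | Top label fits? |
|---|---|---|---|---|
| 5 | noticeability | Noticeable | Noticeable | yes |
| 6 | worry/distress | Worried | Noticeable | no |
| 7 | interference | Interfering | Noticeable | no |

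The middle labels are neutral and identical on all three items. PDF reading is an unlikely cause, because the words are intact and in order on three separate lines, each with its own correct bottom label. The pattern looks like item 5's top label copied forward.

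**2. The plan's own range.** Section 7.11 gives 7 items scored 0 to 4. Maximum = 7 × 4 = 28, which reproduces the stated range.

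**3. Share of the form affected.**

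- Response options: 7 items × 5 options = 35, of which 2 carry a wrong label.
- Points carried by items 6 and 7: 2 × 4 = 8 of 28, or 8/28 = 28.6%.

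**4. Possible shift in one total.** The documents give no data on how respondents read the label. Assumption: it moves an answer by 0 or 1 category on each item. The shift in a total at one visit is then between 0 and 2 × 1 = 2 points, at most 2/28 = 7.1% of the range. Set against the 8-point change in Section 7.11, 2/8 = 25%. That compares a worst case for one person at one visit with a change score, so it is not an estimate for the endpoint.

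**5. What this does to change from baseline.** Three cases, each taking the shift as a true 4 marked as 3 on both items:

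- Shift at both visits: 2 − 2 = 0 points of error in the change.
- Shift at baseline only, because the true answer at follow-up is below 4: improvement understated by 2 points.
- True answer 4 at both visits, but marked 3 only at follow-up: improvement overstated by 2 points.

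The sign is therefore not fixed even when the shift itself runs one way.

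**6. Reach into the analysis.** Section 10.3.1 bases the sample size on the hot flash score alone. Section 10.4 specifies tests for percent change in that score and for a 50% reduction in it. Neither section uses the ISI or the 8-point figure.

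**The case against.** The strongest reply is that this is a clerical slip with little consequence. The questions, bottom labels, middle labels and numbers are all right, and many participants will read the last option as *very much* and mark 4. The same form serves both arms and all three visits, and a participant who marks the same category twice contributes no change on that item whatever the label says. Sleep is also measured by the Pittsburgh index, actigraphy and a diary. All of this stands, and it is why the point is minor.

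Two further arguments also stand. Section 7 plans to collect patient-reported outcomes in REDCap on a tablet, and the documents do not show the labels there. In addition, the plain language summary (Appendix XVI) reports results through week 20, and the notification letter printed after the Appendix XVII survey says the primary analyses are complete. Relabelling the form cannot alter data already collected, and a change during follow-up would mix wordings within a participant.

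What does not stand is the suggestion to drop the point. The mismatch is visible from the form alone, the form feeds a named secondary endpoint, and a reader of the ISI results needs to know which wording was used.

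**Conclusion.** The point holds as a minor form error. Two of 35 response options, on items carrying 8 of 28 points of a secondary endpoint, name the wrong construct. The effect is probably small and similar in both arms, and of unknown size and direction. The figure of 0 to 2 points on an individual total at a visit rests on the one-category assumption, which the documents neither support nor contradict. There is no effect on the primary endpoint, sample size or power.

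A reader might infer more, in three ways that the documents do not support.

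- *That the two items fail to measure worry and interference.* They ask about exactly those things; only the label for score 4 is wrong.
- *That severe scores are compressed and a treatment effect diluted.* No document shows a shift from 4 to 3, and step 5 of the working shows that error in the change could go either way.
- *That the 8-point criterion is undermined.* It appears only as description in Section 7.11, and no planned analysis applies it. Nor can the form be compared with the published instrument, which is cited but not reproduced. Only the inconsistency within the printed form can be established.

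**What to change.** 1. In Appendix XIV, change the top label of item 6 to *Very Much Worried* and of item 7 to *Very Much Interfering*.
2. Check the REDCap version. If it carries the same labels, correct it before it is used with new participants.
3. Where a participant has already completed the form, keep her wording constant across visits.
4. Confirm from the forms or the database build which labels were administered, and report the deviation with the ISI results if the printed labels were used.

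The cost is two labels on one form, one check of the electronic build and a sentence in the report. No analysis changes, and participants carry no extra burden.
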